6.3.3.2 Additional Analysis Methods for Consistency of Primary Efficacy Result

We will investigate two other ITT variants: (1) last-observation-carried-forward (LOCF) and (2) performing a sensitivity analysis in which outcomes will be assigned to missing eyes so as to explore both the minimum and maximum possible estimates of treatment effects. A per-protocol analysis, excluded from which will be those study participants who drop out, cross over to another treatment group, or violate the protocol, also will be conducted including only study eyes that have completed 12-month visual acuity data. Logistic regression analysis will be performed to adjust for any potential imbalances in baseline characteristics observed between treatment groups, with the odds ratio used as a measure of increased or decreased risk.

1626 **6.4 Assumptions for and Result of Sample Size Estimation**1627 **6.4.1 Study Power**

1628 The study power is set for each trial at 80%.

1629

1630 **6.4.2 Estimate of CRVO Primary Efficacy Outcome in the Standard Care Group**1631 The Central Vein Occlusion Study (CVOS) demonstrated that in participants with
1632 macular edema for more than 3 months secondary to a CRVO, macular grid laser
1633 photocoagulation, as compared to no treatment, did not improve visual acuity.⁴ There
1634 were no significant differences between treated and untreated participants in either
1635 level of visual acuity or change in visual acuity across all follow-up visits. The data
1636 from the CVOS demonstrate that at 2 years from baseline 18% of treated eyes (10 of
1637 57 eyes) and 11% of untreated eyes (6 of 53 eyes) experienced a gain of three or more
1638 lines of visual acuity. At 1 year, approximately 6% in both the treated and untreated
1639 eyes showed a gain of three or more lines of visual acuity. From these data, it is
1640 conservatively estimated that approximately 15% of untreated eyes with CRVO will
1641 experience a gain of three or more lines of visual acuity at 1 year.

1642

1643 **6.4.3 Estimate of BRVO Primary Efficacy Outcome in the Standard Care Group**1644 In the Branch Vein Occlusion Study (BVOS), macular grid laser photocoagulation
1645 was demonstrated to be effective in improving visual acuity in some eyes with BRVO
1646 complicated by macular edema.¹ Treatment resulted in a two or more line
1647 improvement in visual acuity for two or more consecutive visits in approximately

6.4.5 Sample Size Estimate

1698 The sample size estimate (number per group) was computed assuming the efficacy in
1699 the two steroid doses are the same. If the efficacy in the 4 mg group is higher than the
1700 1 mg group, and given the other preceding assumptions, the study power will be
1701 higher for the standard care versus 4 mg comparison. This was considered important
1702 because the 4 mg dose is the basis for all available information.

1703

Sample Size Estimate

Type I error (alpha) = .025, study power = 80%

	CRVO	BRVO
--	------	------

Standard care	15%	35%
---------------	-----	-----

1 mg or 4 mg	30%	53%
--------------	-----	-----

N per group	147	147
-------------	-----	-----

The allocation ratio will be 1:1:1 for standard care: 1 mg: 4 mg. The number per group has been increased by 10% to allow for some missing data at 12 months (number per group=162). Thus, the total sample estimate for the CRVO trial is 486 (3 times 162) and for the BRVO trial the total sample estimate is 486 (3 times 162).

6.5 Safety Outcomes

Safety outcomes that will be assessed include serious adverse events and specific ocular events requested by the Data and Safety Monitoring Committee. The SCORE Study DCC and DSMC will continuously monitor the following safety indicator variables:

- Cataract
- IOP exceeding 35 while on maximal medical therapy
- Filtration surgery to lower IOP
- Non-infectious endophthalmitis
- Any of: infectious endophthalmitis, retinal detachment, vitreous hemorrhage, loss of 20 ETDRS letters at 4 days or 4 week post injection, a new-onset retinal arterial occlusion, a transition from a branch to a central retinal vein occlusion, a new, clearly independent branch retinal vein occlusion, or anterior ischemic optic neuropathy.

Table 5 indicates the precision with which the SCORE Study will be able to estimate rates of safety events at the end of the trial. Three sample sizes are provided in Table 5:

- N=162: within each study arm.
- N=324: pooling the 1 mg and 4 mg intravitreal injection arms within CRVO or BRVO disease area OR pooling the 1 mg or 4 mg intravitreal injection arm across each disease area.

1734 • N=648: pooling the 1 mg and 4 mg intravitreal injection arms across each disease
 1735 area.

1736 For example, if the true rate is 0.25 and the sample size is 162, the 10% quantile for the
 1737 lower 95% confidence limits is 0.15, and the 90% quantile for the upper 95% confidence
 1738 limit and half-width are 0.36 and 0.07, respectively.

1739

1740 **Table 5: 90% limits for 95% confidence intervals of rates of safety events,
 1741 as a function of the true rate p and the sample size N**

P	N=162			N=324			N=648		
	Lower CL	Upper CL	Half-width	Lower CL	Upper CL	Half-width	Lower CL	Upper CL	Half-width
0.01	0.00	0.05	0.02	0.00	0.04	0.02	0.00	0.03	0.01
0.03	0.00	0.09	0.04	0.01	0.07	0.02	0.01	0.06	0.02
0.05	0.01	0.13	0.04	0.02	0.10	0.03	0.03	0.08	0.02
0.1	0.03	0.19	0.05	0.05	0.16	0.04	0.06	0.14	0.03
0.15	0.07	0.25	0.06	0.09	0.22	0.04	0.11	0.20	0.03
0.25	0.15	0.37	0.07	0.18	0.33	0.05	0.20	0.31	0.03
0.5	0.37	0.63	0.08	0.41	0.59	0.06	0.44	0.57	0.04

1743 **6.6 Secondary Efficacy Outcomes**

1745 Secondary efficacy outcomes will be analyzed by comparing each triamcinolone group (4
 1746 mg or 1 mg) to standard care as well as by comparing 4 mg vs 1 mg intravitreal
 1747 triamcinolone for the secondary efficacy outcome variables listed below. The secondary
 1748 efficacy outcomes include the following:

- 1749 • Change between baseline and each efficacy outcome assessment visit in best-
 1750 corrected ETDRS visual acuity score (e.g., mean change from baseline in visual
 1751 acuity, distribution of change from baseline in visual acuity based on clinically
 1752 meaningful cut points of improvement or worsening of visual acuity).
- 1753 • Change in calculated retinal thickening as assessed by optical coherence
 1754 tomography.
- 1755 • Change in retinal thickness at the center of the macula as assessed by stereoscopic
 1756 color fundus photography.
- 1757 • Change in area of retinal thickening as assessed by stereoscopic color fundus
 1758 photography.

1759

1760 **6.7 Statistical Guidelines for Interim Monitoring by the DSMC**1761 **6.7.1 Interim Monitoring for Safety**

1762 The SCORE Study will use repeated confidence intervals to continuously monitor the
1763 safety indicator variables mentioned in section 6.5. Safety rates will be reported
1764 separately in the two disease areas, but injection arms will be pooled to increase
1765 accuracy of the estimates.

1766

1767 **6.7.2 Interim Monitoring for Efficacy**

1768 The primary efficacy outcome occurs at 12 months from the randomization visit. The
1769 recruitment pattern is unpredictable. Information concerning the primary outcome
1770 will accrue as participants complete their 12-month visit and thus "information time"
1771 is the percent of the 486 patients in each trial expected to have completed this visit.

1772

1773 Of the Type I error (α) = .05 for each trial, α = 0.005 will be allocated for
1774 interim monitoring and the remaining α = 0.045 will be reserved for the final
1775 analysis. With α = 0.045 for the final analysis, the estimate of the sample size
1776 does not need to be increased for interim monitoring. Interim testing will be carried
1777 out using the Lan-DeMets interim monitoring boundary with an O'Brien-Fleming-
1778 type spending function where at most 0.005 cumulative α can be spent prior to the
1779 final analysis. The "height of the hurdle" is highest when the information fraction is
1780 smallest and decreases as additional patients complete 12 months. The "height of the
1781 hurdle" can be calculated for each DSMC meeting based on the number of patients
1782 expected to have completed the 12-month visit and the α spent by previous
1783 "looks" by the DSMC. With the specification that the total α for interim
1784 monitoring is 0.005, the maximum amount the DSMC can "spend" is 0.005. If the
1785 DSMC looks more often, it will "spend" less per look.

1786

1787 Formally, if t is the information fraction, $B(t)$ is the 2-sided cumulative O'Brien-
1788 Fleming-type spending function of Lan & DeMets with final value $B(1) = 0.005$, and
1789 $S(t)$ is the two-sided cumulative spending function used by SCORE, then

$$1790 S(t) = \begin{cases} B(t) & \text{for } 0 \leq t < 1 \\ 0.05 & \text{for } t = 1 \end{cases}$$

1791
1792 At each interim inspection, the three comparisons will be made using the Lan-DeMets
1793 methodology, and the results combined using Hochberg's sequentially rejective
1794 procedure as described in the MOPP, section 6.4.

1795 **6.7.3 Interim Monitoring for Futility**

1796 The DSMC will consider futility as well as safety and efficacy. One method of
1797 statistically assessing futility is to use conditional power to estimate the likelihood of
1798 statistical significance given the observed efficacy results and various possible
1799 choices for the remaining results.

1800

1801 **6.7.4 Analyses and Results Requested to be Considered Prior to** 1802 **Recommending Early Termination**

1803
1804 Before recommending early termination, the DSMC will consider:

- 1805 • internal consistency of primary and secondary results
- 1806 • internal consistency of primary and secondary results by subgroups
1807 defined by baseline characteristics (e.g. visual acuity categories, categories
1808 based on length of history of CRVO or BRVO, and time period of
1809 enrollment)
- 1810 • distribution of baseline prognostic factors among the three groups
1811 (standard care, 4 mg, 1 mg)
- 1812 • consistency of primary and secondary results across clinical centers and
1813 among centers enrolling larger numbers of patients

1814 • possible bias in assessment of primary and secondary response variables,
1815 particularly visual acuity, given the unmasked implementation of standard
1816 care versus intravitreal triamcinolone
1817 • possible impact of missing data from missed patient visits for assessment
1818 of the primary and secondary response variables
1819 • possible differences in concomitant interventions or medications.

1820 **6.7.5 Study Timeline and DSMC Data Reviews**

1821 The DSMC will meet to review study data starting in November 2004, and every 6
1822 months until 3-year follow-up is concluded on all study participants. Table 6 depicts
1823 the fractions of the population enrolled, with 1 year follow-up, and with 3 year
1824 follow-up, assuming that enrollment is constant, starts in August 2004, and takes 18
1825 months. Under this assumption, there will be 10 DSMC meetings. Formal interim
1826 inspection for 1-year efficacy will take place only during the four meetings when the
1827 information fraction is nonzero, that is, in November and May of 2005 and 2006.

1828 **Table 6: Study Timeline for DSMC Data Reviews**

1829 Date of DSMC Meeting	1830 Fraction		
	1831 Enrolled	1832 With 1-year 1833 follow-up	1834 With 3-year 1835 follow-up
November 2004	2/9		
May 2005	5/9		
November 2005	8/9	2/9	
May 2006	1	5/9	
November 2006		8/9	
May 2007		1	
November 2007			2/9
May 2008			5/9
November 2008			8/9
May 2009			1

1832 7. Confidentiality and Access to Source Data / Documents

1833 The investigators will maintain the highest degree of confidentiality permitted for the clinical and
1834 research information obtained from participants in this clinical study. Medical and research
1835 records should be maintained in the strictest confidence. However, as part of the quality
1836 assurance and legal responsibilities of an investigator, the site must permit authorized
1837 representatives of the sponsor(s), the SCORE Coordinating Center, and regulatory agencies to
1838 examine (and when permitted or required by applicable law, to copy) clinical records for the
1839 purposes of quality assurance reviews, audits and evaluation of the study safety and progress.
1840 Unless required by the law, no copying of records with personally identifying information will be
1841 permitted. Only the coded identity associated with documents or other participant data may be
1842 copied (obscuring any personally identifying information) or transmitted to the SCORE
1843 Coordinating Center. Authorized representatives as noted above are bound to maintain the strict
1844 confidentiality of medical and research information that may be linked to identified individuals.
1845 The site will normally be notified in advance of monitoring and auditing visits.

1846

1847 8. Summary of Good Clinical Practice Compliance

1848 This trial will be conducted in accordance with Good Clinical Practice (GCP) using the guidance
1849 documents and practices offered by ICH and FDA, and in accordance with the Declarations of
1850 Helsinki and the policies and procedures for the SCORE Coordinating Center at The EMMES
1851 Corporation. This study will also comply with the regulations under 21 CFR Parts 50, 54, 56,
1852 and 312 under an IND application authorized by FDA.

1853

1854 8.1 Investigator Responsibilities (Form FDA-1572)

1855 A Statement of Investigator (Form FDA-1572) including the names of all of the
1856 sub-investigators and selected key study personnel (e.g., pharmacist, study nurse and/or
1857 study Coordinator, ophthalmic technician or optometric staff may be listed if desired)
1858 directly involved in the study will be completed and signed by the Principal Investigator at
1859 each site. The general responsibilities of the Investigator as acknowledged on the Form
1860 FDA-1572 are governed under the regulations in 21 CFR Parts 50, 54, 56, 312, and HIPAA.
1861 The study drug or test article may be administered only in accordance with the approved
1862 protocol and under the supervision of the Investigator or a sub-investigator listed on this

1863 form. The Investigator must maintain accurate and complete study records, including
1864 records for disposition of the test article, and an accurate and complete record of all
1865 submissions made to and received from the local Institutional Review Board (IRB) or
1866 Independent Ethics Committee (IEC), including a copy of all reports and documents
1867 submitted. Adverse experiences that are reported to the FDA as IND Safety Reports must
1868 be submitted promptly to the local IRB/IEC and the SCORE Coordinating Center.

1869
1870 Progress reports must be submitted by the Investigator to the IRB/IEC at least once per
1871 year. The IRB/IEC must be promptly notified of completion or termination of the study.
1872 Within three months of study completion or termination, a final report from the Investigator
1873 must be provided to the IRB/IEC.

1874
1875 The curriculum vitæ (CV) or a résumé for each investigator, sub-investigator, and key study
1876 personnel must also be supplied if named on the Form FDA-1572. This form and related
1877 CVs must be supplied to the SCORE Coordinating Center prior to initiating the trial at each
1878 site. When necessary due to personnel changes, updated versions of the Form FDA-1572
1879 must be forwarded to the SCORE Coordinating Center and copies of all versions must be
1880 maintained in study records at each site. Any CV or résumé collected at the beginning of a
1881 study should be current, and would need to be updated during the study only if substantial
1882 changes or additions are warranted (e.g., change of position or affiliation, certifications or
1883 licensure, or significant new publications relevant to the study protocol).

1884
1885 **8.2 Human Subjects Protection**

1886 **8.2.1 Institutional Review Board or Independent Ethics Committee**

1887 Each participating institution must have an IRB or IEC constituted and operating in
1888 accordance with the regulations under 21 CFR Part 56 and authorized by the
1889 institution to review and approved materials for this trial. Because of the use of US
1890 Federal funds in this trial, all participating institutions must have a current Assurance
1891 of Compliance (either FWA or MPA) regarding their IRB/IEC on file with the DHHS
1892 Office of Human Research Protections (OHRP) before any award can be made to that

1893 institution and before participants may be enrolled in the trial. In addition, each
1894 reviewing IRB or IEC must be registered with OHRP. A list of IRB/IEC voting
1895 members, their titles or occupations, and their institutional affiliations, as well as a
1896 copy of the Assurance of Compliance, must be kept available by the institution for
1897 inspection and copying by authorized study monitors, auditors, and regulatory
1898 officials.

1899

1900 **8.3 Data Handling and Recordkeeping**

1901 The Principal Investigator at the Participating Clinical Center is responsible for maintaining
1902 adherence to study procedures within the clinic. He or she must spend adequate time at the
1903 clinic observing study procedures and must hold regular discussions with staff, either
1904 one-to-one or in-group meetings, to review various aspects of the study and to solve
1905 problems that may arise. Other clinic staff members have a responsibility to report to the PI
1906 problems that could affect the quality of the data. The PI will designate one staff member
1907 to be the Clinic Coordinator for the clinic, with specific responsibility for reporting
1908 problems that have affected or can potentially affect the quality of data collected.

1909

1910 The Clinic Coordinator should be thoroughly familiar with clinic activities and equipment
1911 and the MOPP. The Clinic Coordinator should maintain an up-to-date copy of the MOPP
1912 close at hand and encourage all clinic personnel to consult it frequently. During Full Group
1913 Meetings the Clinic Coordinators will have the opportunity to meet with the Protocol
1914 Monitor to discuss mutual problems.

1915

1916 **8.3.1 Case Report Forms**

1917 Clinical data will be entered on electronic Case Report Forms (CRFs) in accordance
1918 with the procedures specified in the current MOPP and Data Management Handbook
1919 (DMH) for this trial.

1920

1921 **8.3.2 Data Transmittal**

1922 The primary method of data transmittal to the SCORE Coordinating Center will be via
1923 the secure AdvantageEDC maintained by The EMMES Corporation. The current

1924 MOPP, DMH and access to the AdvantageEDC are available to authorized users via
1925 the SCORE DCC Internet web site, located at <http://www.emmes.com/> where an
1926 assigned username and password are required for access. All data transfers between
1927 the investigational site and SCORE DCC via the AdvantageEDC are encrypted using
1928 SSL technologies to assure confidential data transfer.

1929

1930 **8.4 Professional Licensure**

1931 Physicians must provide evidence of current medical licensure applicable to the study
1932 location(s) if they are practicing medicine and undertake to diagnose and/or treat
1933 participants (including administration of the test article) in this study. A physician who is a
1934 site Principal Investigator must also provide evidence of ophthalmology training before
1935 study initiation.

1936

1937 **8.5 Human Subjects Protection Training**

1938 Documented training is required for each of the key personnel in the ethical conduct of
1939 clinical studies and in the protection of human subjects.

9. References

1. The Branch Vein Occlusion Study Group. Argon laser photocoagulation for macular edema in branch vein occlusion. *Am J Ophthalmol* 1984;98:271-282.
2. Central Vein Occlusion Study Group. Baseline and early natural history report. The Central Vein Occlusion Study. *Arch Ophthalmol* 1993;111:1087-1095.
3. The Central Vein Occlusion Study Group. Natural history and clinical management of central retinal vein occlusion. *Arch Ophthalmol* 1997;115:486-491.
4. The Central Vein Occlusion Study Group. Evaluation of grid pattern photocoagulation for macular edema in central vein occlusion. The Central Vein Occlusion Study Group M Report. *Ophthalmology* 1995;102(10):1425-1433.
5. Opremcak EM and Bruce RA. Surgical decompression of branch retinal vein occlusion via arteriovenous crossing sheathotomy. A prospective review of 15 cases. *Retina* 1999;19:1-5.

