666 • 4 mg triamcinolone acetonide intravitreal injections with 1 mg triamcinolone
667 acetonide intravitreal injections

668

669 **4.1.2 Secondary Efficacy Outcomes**

670 Secondary efficacy outcomes include the following:

671 • Change between baseline and each efficacy outcome assessment visit in
672 best-corrected ETDRS visual acuity score (e.g., mean change from baseline
673 in visual acuity, distribution of change from baseline in visual acuity based
674 on clinically meaningful cut points of improvement or worsening of visual
675 acuity).

- 676 • Change in calculated retinal thickening as assessed by optical coherence
677 tomography.
- 678 • Change in retinal thickness at the center of the macula as assessed by
679 stereoscopic color fundus photography.
- 680 • Change in area of retinal thickening as assessed by stereoscopic color fundus
681 photography.

682

683 4.2 Safety Assessments

684 4.2.1 Safety Outcomes

685 Safety outcomes will be tabulated by observing the nature, severity and frequency of
686 adverse events throughout the three years of the study. Specific safety outcomes
687 include:

- 688 • Injection-related events including infectious endophthalmitis, non-infectious
689 endophthalmitis, retinal tear or detachment, vitreous hemorrhage, ocular
690 discomfort/irritation, ocular tenderness, ocular itching sensation, foreign
691 body sensation, blurred vision, floaters, corneal abrasion, subconjunctival
692 hemorrhage, conjunctival edema, and conjunctival hyperemia/erythema.
- 693 • Steroid-related toxicities including cataract and elevated IOP.

694

695 4.3 Inclusion Criteria

696 4.3.1 General Inclusion Criteria

- 697 a. Ability and willingness to provide informed consent.
- 698 b. Sex: Participants may be male or female.
- 699 c. Age: 18 years or older

700

701 4.3.2 Ocular Inclusion Criteria (study eye)

- 702 a. Participants must have center-involved macular edema secondary to
703 either CRVO or BRVO. Eyes may be enrolled as early as the time
704 diagnosis of the macular edema, but not longer than 24 months after

705 diagnosis (by patient history or ophthalmologic diagnosis). The
706 following definitions are used for the purposes of the SCORE Study:
707 i. A CRVO is defined as an eye that has retinal hemorrhage or other
708 biomicroscopic evidence of retinal vein occlusion (e.g.
709 telangiectatic capillary bed) and a dilated venous system (or
710 previously dilated venous system) in all 4 quadrants.

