1242 cataract surgery provides a reasonable likelihood of improvement.

1243 2. Lens opacity that inhibits optimal management of posterior segment disease.

1244 3. The lens causes inflammation (phakolysis, phakoanaphylaxis), angle
1245 closure, or medically unmanageable open-angle glaucoma.

1246

1247 *Participants in both the intravitreal steroid groups and the standard care groups
1248 should be assessed for the development of cataract in a similar fashion. Cataract
1249 surgery may be performed at any time that this is indicated clinically.*

1250

1251 **4.9.4 Surgery for Proliferative Retinopathy and Other Complications Due to
1252 Retinal Vein Occlusion**

1253 It is expected that some study participants will develop vitreous hemorrhage and/or
1254 other complications of retinal vein occlusion that may cause visual impairment.

1255 Vitrectomy for the complications of proliferative retinopathy such as vitreous
1256 hemorrhage should be delayed, if clinically feasible, because vitreous hemorrhage
1257 may resolve, obviating the need for vitrectomy. Furthermore, vitrectomy is thought to
1258 reduce the half-life of intravitreal steroids such that participants assigned to the
1259 steroid treatment arms may experience reduced benefit from intravitreal steroid
1260 injections following vitrectomy.

1261

1262 A suggested treatment plan that may be followed for eyes with vitreous hemorrhage
1263 and/or other complications of retinal vein occlusion is as follows:

1264 1. Eyes with visually significant, non-clearing vitreous hemorrhage should
1265 have vitrectomy performed if there is no significant clearing in 3 months.

1266 2. Eyes with traction retinal detachment involving or threatening the fovea
1267 should have vitrectomy performed as soon as clinically indicated.

1268 3. Eyes with a combined traction-rhegmatogenous retinal detachment should
1269 have vitrectomy performed as soon as clinically indicated.

1270 4. Eyes with extensive and progressive fibrovascular proliferation should have
1271 vitrectomy performed as soon as clinically indicated.
1272 5. Eyes with vitreoretinal interface disease such as from vitreomacular traction
1273 or an epiretinal membrane can, at the discretion of the investigator, have
1274 vitrectomy performed if the investigator believes that the primary cause of
1275 macular edema and reduced visual acuity is due to the vitreoretinal interface
1276 disease.

1277

1278 **4.10 Miscellaneous Treatments During Follow-up**

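### In the formal safety monitoring, infectious endophthalmitis has no interval of its own: it is followed only inside an eight-part composite, where an excess is diluted

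*Combined protocol and SAP*

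**What the plan says.** Section 6.5 names five indicators for continuous monitoring: cataract; IOP above 35 on maximal medical therapy; filtration surgery; "Non-infectious endophthalmitis"; and a composite. The composite reads "Any of: infectious endophthalmitis, retinal detachment, vitreous hemorrhage, loss of 20 ETDRS letters at 4 days or 4 week post injection", followed by new retinal arterial occlusion, "a transition from a branch to a central retinal vein occlusion", a new independent branch occlusion, and anterior ischemic optic neuropathy. That is infectious endophthalmitis plus seven other event types.

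Section 6.7.1 gives the method: "The SCORE Study will use repeated confidence intervals to continuously monitor the" section 6.5 indicators. Rates are reported "separately in the two disease areas, but injection arms will be pooled to increase" accuracy. No reference rate, threshold or confidence level is stated there. The sample sizes in section 6.5 start from "N=162: within each study arm"; two injection arms within one disease give 324.

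Other sections treat the event individually:
- Section 2.6.3 raises the possibility that an immunosuppressive drug bolus increases post-injection endophthalmitis, and undertakes to monitor its frequency carefully.
- Section 3 makes its incidence a secondary objective.
- Section 4.2.1 names it as a specific safety outcome.
- Section 5.1 has the DSMC review all accumulating data, adverse events included, at least every six months. It also receives certain events case by case, as listed in a separate operating procedure.

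On vitreous hemorrhage, section 4.9.4 says: "It is expected that some study participants will develop vitreous hemorrhage and/or" other complications of the vein occlusion.

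**The concern.** The repeated confidence interval is the only statistical safety-monitoring tool in the plan. For infectious endophthalmitis it is computed on a sum that includes events the vein occlusion or other vascular disease can produce without any injection. The plan expects at least one of these, vitreous hemorrhage, to occur.

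Two consequences follow. First, background events raise both the level and the sampling error of the composite, so a given excess of infections is harder to see. Second, a high composite cannot be attributed to infection without a breakdown, and the plan does not ask for one.

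The allocation of rows is also hard to square with the protocol's own account. Section 2.6.3 calls the non-infectious form usually self-limiting and says the infectious form needs immediate treatment, yet only the non-infectious form has its own indicator.

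The 20-letter item raises a separate labeling matter. It is defined at 4 days and 4 weeks post injection, and section 4.8.1 schedules those visits only after injections. The composite therefore has a component that an uninjected eye cannot contribute.

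**Working it through.** **Inputs.** From the documents: N = 162 per arm, so 2 × 162 = 324 injected eyes per disease area (6.5, 6.7.1). Assumed, because the documents give no values: reference (tolerable) rate 0.5%; true rate 2%; rate b of eyes with another composite event but no infectious endophthalmitis, 0.5% to 8%; one look at full N; ordinary 95% limits.

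**The plan's own figures.** Table 5 gives the 10% and 90% quantiles of 95% confidence limits. With exact binomial quantiles and Clopper-Pearson limits, p = 0.01 and N = 324 give counts of 1 and 6, hence a lower limit of 0.0001, an upper limit of 0.040 and a half-width of 0.017. The table shows 0.00, 0.04 and 0.02. Over the whole table 61 of 63 cells agree within rounding, and the largest difference is 0.006. The same kind of interval is used below.

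**Formula.** Let L(x) be the Clopper-Pearson lower 95% limit for x eyes in 324, that is, the 2.5% quantile of Beta(x, 324 − x + 1). For the event alone, find the smallest count c with L(c) > 0.005; the chance of a flag is P(X ≥ c) with X ~ Bin(324, 0.02). For the composite, find the smallest c with L(c) > b + 0.005, with X ~ Bin(324, b + 0.02).

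**Example.**
- Alone: 324 × 0.005 = 1.6 eyes expected at the reference and 324 × 0.02 = 6.5 at the true rate. L(5) = 0.00503 > 0.005, so c = 5 and P(X ≥ 5) = 0.777.
- Composite with b = 3%: 324 × 0.035 = 11.3 eyes at the reference and 324 × 0.05 = 16.2 at the true rate. L(19) = 0.0357 > 0.035, so c = 19 and P(X ≥ 19) = 0.270. The extra eyes are the same 4.9 in both cases.

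| Other events b | Flag at c eyes | Chance of flag, true 2% | Chance of flag, true 3% |
|---|---|---|---|
| none (alone) | 5 | 78% | 97% |
| 0.5% | 8 | 56% | 88% |
| 1% | 11 | 38% | 75% |
| 3% | 19 | 27% | 57% |
| 5% | 27 | 20% | 44% |
| 8% | 39 | 13% | 30% |

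When the rate is truly at the reference, every row flags with probability below 2.5%, so the loss is not a trade against false alarms.

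**Sensitivity (true 2%).**
- Reference 1% instead of 0.5%: alone c = 8, chance 32%. Composite with b = 0.5%, 1%, 3%, 5%, 8%: c = 11, 13, 21, 29, 41; chances 19%, 18%, 14%, 11%, 7%.
- 99% limits as a rough stand-in for wider repeated intervals, reference 0.5%: alone c = 7, chance 47%. Composite: c = 10, 12, 22, 30, 42; chances 29%, 27%, 9%, 7%, 5%.
- Interim N = 100, event alone, reference 0.5%: 32% with 95% limits and 14% with 99% limits.

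The ordering is the same in both sensitivity sets that include the composite. The levels move a great deal.

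**The case against.** **Other monitoring exists.** A reader might infer that infectious endophthalmitis is monitored nowhere else, so that cases could pass unnoticed. The documents do not support this. Sections 2.6.3, 3, 4.2.1 and 5.1 handle the event individually, and section 5.2 requires serious events to reach the coordinating center within 24 hours. Whether the DSMC's case-by-case list includes it cannot be judged, because that procedure lies outside the documents. What stands is narrower: none of these provisions commits anyone to an interval on this event's rate.

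**Causes are mixed.** A reader might also infer that the composite is dominated by background disease and short-lived post-injection blur. The plan gives no rate for any component and does not call the 20-letter loss temporary. The Précis and section 4.2.1 list vitreous hemorrhage as injection-related, section 4.9.4 lists traction detachment as a vein-occlusion complication, and section 2.3 calls injection-related events rare in earlier series. Some components can arise from the disease; how much of the composite they make up is unknown.

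**No comparison is specified.** It is tempting to say that the composite lacks a valid standard-care comparator, or is faulty because branch-to-central transition applies only to branch occlusion. Section 6.7.1 states neither a standard-care nor a cross-disease comparison, so no error follows. The injected-eyes point calls for a label.

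**The numbers are chosen.** This is correct. The plan has no flagging rule, and the calculation lets only endophthalmitis rise; if injection raised several components together, pooling could help. Low background rates soften the contrast (56% or 38%). A two-arm Fisher test of 324 against 162 eyes, with no control infections, has 20% power for a 2-point excess alone against 6% to 13% in a composite with background 3% to 15%; for a 1-point excess it has almost none either way.

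**The DSMC asked for these events.** Section 6.5 says its safety outcomes include ocular events that the DSMC requested. That is a reason to keep the composite. It does not argue against an added row.

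**Conclusion.** The point holds in a limited form. Within sections 6.5 and 6.7.1, infectious endophthalmitis is followed only as one of eight composite events, while the non-infectious form has its own indicator and section 2.6.3 promises attention to the infectious form's frequency. Cases are visible elsewhere, so this is a loss of sharpness in one monitoring tool and not a failure of safety oversight.

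The direction of the loss follows from adding other events to the count when only the infection rate rises. Its size is conditional: 78% alone against 13% to 56% in the composite, for a true 2%, a reference of 0.5%, other events at 8% down to 0.5%, and a single look at 324 eyes. These figures should not be read as the trial's actual detection probabilities. A 1% reference gives 32% alone, and wider repeated intervals or earlier looks lower every figure. The change is worth making because it is cheap and the event is grave, not because a particular power is at stake.

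**What to change.** In section 6.5, list infectious endophthalmitis as a separate indicator beside the non-infectious form, with its own section 6.7.1 interval in each disease area. Keep the composite as it stands, but report it to the DSMC with a count for each component. Label the 20-letter loss at day 4 or week 4 as defined for injected eyes only.

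This needs no new data, since the component events are already collected. The cost is wording in section 6.5 and a few more rows and intervals in the safety report. Some rows will hold very few events and say little: Table 5 itself shows a lower limit of 0.00 at a true rate of 1% with 324 eyes. Each added interval also brings its own chance of a false signal, which the DSMC should keep in mind when reading them.
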